5.1 Inclusion Criteria

In order to be eligible to participate in this study, an individual must meet all of the following criteria:

1. Female, between the age of 18 and 80
2. OD symptoms as indicated by an affirmative response to either questions 7, 8 or 14 of the Pelvic Floor Distress Inventory (PFDI):
 - a. Do you feel you need to strain too hard to have a bowel movement?
 - b. Do you feel you have not completely emptied your bowels at the end of a bowel movement?
 - c. Does part of your bowel ever pass through the rectum and bulge outside during or after a bowel movement?
3. Rectal hypermobility defined as a compression ratio greater than 50% according to ultrasound
4. Patient planning on undergoing surgery for the repair of pelvic organ prolapse within the next 12 months
5. Patient who is not pregnant and does not intend to become pregnant in the next 2 years
6. Available for 24-months of follow-up
7. Stated willingness to comply with all study procedures and availability for the duration of the study
8. Able to complete study assessments, per clinician judgment
9. Able and willing to provide independent written informed consent

10. Stable cardiovascular and respiratory status to meet candidacy in vaginal or laparoscopic surgeries

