9.2 Sample Size Determination

Based on our preliminary studies in literature (83-87), we assume an anatomic success rate in LAVR group is about 70% at 24 months. The investigators believe that a difference in success rates less than 25% will not change clinical practice, but also that the sample size should be large enough so that an observed difference in success rates of 20% would be significant; i.e., an inability to differentiate between the procedures will require an observed difference that is less than 20%.

The study will be individually randomized group-treatment trial (IRGT), which patients are randomized to surgical interventions through a common surgeon (88-90). There will be three surgeons performing each surgical treatment. The number of surgeons and patients will be the same in each clinical site. We anticipate an average of 16 individually randomized patients per surgeon in each treatment group. Outcomes for patients treated by the same surgeon tend to be more similar. We assume minimal variability, estimating a small intraclass correlation coefficient (ICC) of 0.01. The table below illustrates power to detect at least 23% difference between treatment groups with varying assumptions on ICC and dropout rates. A total of 96 patients (48 patients per group) would yield 86% power to differentiate between anatomical success rates of 70% and 93% assuming an ICC of 0.01 and a two-sided 5% level of significance. Projecting a 20% dropout/loss to follow up rate over 2 years, we anticipate recruiting and up to 120 total patients.

ICC	% Dropout	Total patients	Average patients per surgeon	Power
0.01	0	120	20	92%
	10	108	18	90%
	20	96	16	86%
0.02	0	120	20	90%
	10	108	18	87%
	20	96	16	83%
0.05	0	120	20	82%
	10	108	18	79%
	20	96	16	76%

Due to concerns that ICC is higher than expected or dropout rate is higher than 20% toward the end of 2-year follow-up, we calculated the sample size that would be needed for 87% power to differentiate between anatomical success rates of 70% and 95% (a difference of 25%) in treatment groups with a two-sided 5% level of significance. The required sample size is 39 per group, or 78 total patients.

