9.4.2 Analysis of the Primary Efficacy Endpoint(s)

Anatomical Surgical Outcome

The primary endpoint for the surgical treatment is dichotomous: success or failure at 24 months after surgery. The primary outcome measure uses the rectal compression ratio at 24 months unless there has been retreatment at an earlier time. When there is retreatment, or when the 24-month ultrasound results and POPQ results are missing and the last observed measurements were consistent with the definition of failure, then the results at 24 months will be imputed to be a failure. A sensitivity analysis will be performed to study the effect on the primary endpoint of different methods of handling dropouts and missing data. It will be conducted by assuming various values for the imputed outcomes and comparing the results under those assumptions to the results of the primary analysis.

Cochran-Mantel-Haenszel (CMH) test will be used to compare between surgical treatments adjusting for stratification factor. In addition, Generalized linear mixed-effects models (GLMMs) will be performed to yield an effect estimate of conditional on surgeon. Demographics and other characteristics at baseline (treatment group, age, BMI, menopausal status, parity, duration and severity of ODS) will be included. Surgeon will be included as a random effect to account for

correlation between outcomes of patients treated by the same surgeon. Adjusted odds ratios (ORs) will be presented with 95% confidence intervals (CIs).

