9.4.5 Baseline Descriptive Statistics

A summary table with descriptive statistics will be generated for baseline characteristics, including demographics and laboratory measurements based on the ITT population. Baseline characteristics will be presented by intervention groups in a table, but no formal statistical hypothesis testing will be performed. Continuous variables will be summarized using mean with standard deviation or median with interquartile range. Categorical variables will be summarized using frequency and percentage.

Baseline characteristics include demographics, medical history, surgical history, physical exam, pelvic ultrasound, MR defecography, POPQ, PFDI, Pain Scale, Assessment of pain medication use, and Activity assessment scale.

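### Neither primary-endpoint analysis in 9.4.2 adjusts for screening compression ratio, the outcome's own baseline value; prespecifying it is a cheap, minor improvement

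*Combined protocol and SAP*

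**What the plan says.** Section 3 (Outcomes and Measurements) and section 8.1 define surgical failure as a compression ratio above 20% on ultrasound. Section 9.4.2 makes the primary endpoint success or failure at 24 months, with retreatment also counted as failure. It names two analyses:

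- a CMH test between treatments, adjusted for the stratification factor (section 6.3 prepares a separate randomisation schedule for each site);
- in addition, a generalised linear mixed model (GLMM) with surgeon as a random effect, for which the text says "Demographics and other characteristics at baseline (treatment group, age, BMI, menopausal status, parity, duration and severity of ODS) will be included".

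The same measurement exists before surgery for every randomised woman. Section 5.1 requires "Rectal hypermobility defined as a compression ratio greater than 50% according to ultrasound". The Schedule of Activities puts the dynamic ultrasound at screening. Section 9.4.5 tabulates it: "Baseline characteristics include demographics, medical history, surgical history, physical exam, pelvic ultrasound, MR defecography, POPQ, PFDI, Pain Scale".

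Sections 9.4.3 and 9.4.7 reuse the primary-endpoint model or method for the symptom endpoint and the subgroups. Section 9.4.1 leaves implementation to a SAP to be written before database lock.

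**The concern.** When an endpoint is a follow-up measurement cut at a threshold, the baseline value of that measurement is the natural first covariate. Women can enter anywhere above 50%, and one who starts well above that may be less likely to finish at or below 20%. The GLMM list holds six baseline characteristics but not this one.

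The term for severity of ODS does not clearly fill the gap. It is not defined as the compression ratio anywhere, and section 4.2 treats the ratio as a predictor of symptom severity, which makes them separate quantities. The ratio is not among the subgroup variables in 9.4.7 either.

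Two things are at stake. The first is protection of the treatment estimate against a chance difference in starting hypermobility, with about 48 evaluable women per arm. The second is possibly some power.

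**Working it through.** **Inputs.** From 9.2: success 70% v 93%; 48 evaluable per arm; stated power 86%, "assuming an ICC of 0.01 and a two-sided 5% level of significance"; 16 women per surgeon. From 4.2 (case series of 20): preoperative ratio mean 45.5, SD 18.4. Assumed, because the documents do not give it: the correlation r between the screening ratio and the 24-month outcome.

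**1. The plan's own power figure.** Design effect = 1 + (16 − 1) × 0.01 = 1.15, so effective n = 48/1.15 = 41.7 per arm.
- Pooled: Φ[(0.23 − 1.96 × 0.0850)/0.0812] = 78.3%.
- Unpooled: Φ[0.23/0.0812 − 1.96] = 80.9%. Arcsine: 81.3%.
- Unpooled with clustering ignored: Φ[0.23/0.0757 − 1.96] = 86.0%.

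The stated 86% therefore does not follow from the stated two-sided alpha and ICC. That is a separate matter. Here it means that gains are shown at both n = 48 and n = 42 per arm.

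**2. Effect of the entry rule on r.** A normal variable (45.5, SD 18.4) truncated to 50–100 has mean 63.0 and SD 10.0, so it keeps 29.4% of the variance (u² = 0.294, u = 0.543). The within-trial correlation is r·u/√(1 − r² + r²u²).
- Unrestricted 0.5: 0.271/√(0.75 + 0.074) = 0.30.
- Unrestricted 0.3: 0.163/√(0.91 + 0.026) = 0.17.

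**3. Power with and without the ratio.** Logistic likelihood-ratio test for treatment, failure rates held at 30% v 7%, 6,000 simulated trials per setting (Monte Carlo error about 0.5 point). Clustering enters only through effective n, and the other covariates are left out.

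| Within-trial r | 42 per arm | 48 per arm |
|---|---|---|
| 0 | 81.2% → 81.4% | 86.8% → 86.4% |
| 0.2 | 82.6% → 83.4% | 87.2% → 87.8% |
| 0.3 | 80.9% → 83.6% | 86.9% → 88.8% |
| 0.5 | 81.0% → 88.3% | 86.9% → 91.9% |

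A separate simulation (2,500 trials, 48 per arm) gave 87.1% → 88.3% at r = 0.3 and 86.1% → 91.0% at r = 0.5. Rejection under 70% v 70% stayed between 4.6% and 5.9%.

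**4. Chance imbalance.** With SD 10, the standard error of the between-arm difference in screening ratio is 10 × √(2/48) = 2.0 points. A difference of up to 1.96 × 2.0 ≈ 4 points, or 0.4 SD, is within ordinary chance.

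**5. Room in the model.** Expected failures are 48 × 0.30 + 48 × 0.07 = 14.4 + 3.4, about 18. The GLMM already has seven fixed terms (treatment plus six) and a surgeon effect.

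**The case against.** The strongest reply is that adding the ratio to the GLMM does nothing for the comparison that 9.4.2 names first. The CMH test adjusts for the stratification factor only, and the GLMM is run in addition. This stands: a power gain needs the adjusted model to be made the primary test.

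Second, the prognostic value of the ratio within this trial is assumed. No baseline-to-follow-up correlation is reported. The predictive evidence in 4.2 relates the ratio to symptoms, with a cut-off of 14, far below this trial's entry range. Severity of ODS may also carry part of the same information, and the simulations compare a model containing the ratio alone with no covariates at all. So the increment over the planned GLMM could be smaller than tabulated. This also stands.

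Third, 9.4.1 compares baseline measures to identify imbalances, and the SAP is still open. That would reveal an imbalance, but nothing says what would follow. Adding the ratio after seeing the data, with surgeons and participants unmasked (6.3), would be open to criticism.

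A reader might go further and infer that the trial gives up substantial power, for example by taking r = 0.5 and cutting the variance by 1 − r² = 25%, which moves 86% to 94%. The documents do not support that. The formula belongs to a continuous outcome and this endpoint is binary. At the same r the simulations gain about 5 points with 48 per arm. Under the assumed pilot SD, entry above 50% also shrinks an unrestricted 0.5 to about 0.3.

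**Conclusion.** The omission is certain: the outcome's own baseline value is collected for every randomised woman and used in neither primary-endpoint analysis. The benefit of adding it is small and conditional. In the GLMM alone it protects the adjusted odds ratio against chance imbalance and leaves the CMH test as it is. If the adjusted model were made the primary test, power would rise by about 0 to 3 points for a within-trial correlation up to 0.3, and by about 5 to 7 points only if that correlation reached 0.5. These figures rest on an assumed correlation, on the pilot SD of 18.4 applying to the source population, and on a simulation without the other covariates. If the ratio turns out not to be prognostic, the cost in power is negligible. This is a cheap improvement of minor weight, not a flaw that threatens the primary conclusion.

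**What to change.** In 9.4.2 and the SAP:

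1. Prespecify screening ultrasound compression ratio, as a continuous covariate, in the GLMM.
2. With about 18 expected failures, put it in place of a less prognostic listed term so that the model stays at seven fixed terms. The documents do not rank the listed covariates, so the sponsor should choose and justify the term to remove before seeing outcome data.
3. Carry the same covariate wherever the model is reused (9.4.3, 9.4.7).
4. State whether the CMH test or the covariate-adjusted model is the primary test. This is needed either way, and it decides whether any power is gained.

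The cost is a few lines of wording and no new data. The downside is that one listed covariate is swapped out. Naming the adjusted model as primary would be a larger change than the covariate itself and should be decided on its own merits.

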9.4.3 Analysis of the Secondary Endpoint(s)

Subjective Surgical Outcome

The secondary endpoint is the presence of OD symptoms (yes/no) at 24 months after surgery. Questionnaires that assess the presence and severity of OD symptoms include pain/activity assessment scale, global improvement in bladder function, prolapse and colorectal symptoms as assessed by POPDI, CRADI, UDI, quality of life by PFIQ, SF-36, EQ-5D, and pelvic muscle strength measured by Brink Scale. Differences between surgical treatments will be analyzed using generalized linear mixed-effects models, as described for the primary endpoint. However, imputation of missing values will not be done for secondary measures.

Validation

There will be two forms of validation: statistical and radiological. For statistical validation, we expect to see a significant and positive correlation between measurements of the Compression ratio between the two modalities. However, since the Compression ratio as measured via MR defecography is not used clinically to diagnose abnormalities in rectal support (rectal prolapse or rectal intussusception), this does not validate the use of ultrasound for diagnostic purposes. Thus, radiological validation will be performed where the Compression ratio is also correlated with a radiologist's diagnosis of an abnormality in rectal support.

9.4.4 Safety Analysis

Any endpoints that relate to safety will be analyzed using methods previously described.

All adverse events collected will be coded. Events will be summarized cumulatively through the following time points: 2 weeks, 2 months, 12 months, and 24 months postoperatively. Severity and frequency of AEs will be presented. In addition, the frequency and percentage of participants who had a Serious AE (SAE) or a related AE will be tabulated separately.

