- **Not Related** – The AE is completely independent of study intervention administration, and/or evidence exists that the event is definitely related to another etiology. There must be an alternative, definitive etiology documented by the clinician.

[8.3.3.3 Expectedness](#)

Principal investigator and co-investigators will be responsible for determining whether an adverse event (AE) is expected or unexpected. An AE will be considered unexpected if the nature, severity, or frequency of the event is not consistent with the risk information previously described for the study intervention.

[8.3.4 Time Period and Frequency for Event Assessment and Follow-up](#)

The occurrence of an adverse event (AE) or serious adverse event (SAE) may come to the attention of study personnel during study visits and interviews of a study participant presenting for medical care, or upon review by a study monitor.

All AEs including local and systemic reactions not meeting the criteria for SAEs will be captured on the appropriate case report form (CRF). Information to be collected includes event description, time of onset, clinician's assessment of severity, relationship to study product (assessed only by those with the training and authority to make a diagnosis), and time of resolution/stabilization of the event. All AEs occurring while on study must be documented appropriately regardless of relationship. All AEs will be followed to adequate resolution.

Any medical condition that is present at the time that the participant is screened will be considered as baseline and not reported as an AE. However, if the study participant's condition deteriorates at any time during the study, it will be recorded as an AE.

Changes in the severity of an AE will be documented to allow an assessment of the duration of the event at each level of severity to be performed. AEs characterized as intermittent require documentation of onset and duration of each episode.

PI and co-investigators will record all reportable events with start dates occurring any time after informed consent is obtained until 7 (for non-serious AEs) or 30 days (for SAEs) after the last day of study participation. At each study visit, the investigator will inquire about the occurrence of AE/SAEs since the last visit. Events will be followed for outcome information until resolution or stabilization.

[8.3.5 Adverse Event Reporting](#)

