9.3 Populations for Analyses

Modified Intent-to-treat (mITT) Population

The mITT population will include all randomized participants who received at least one post-op visit. Participants will be analyzed according to their randomized treatment assignment, regardless of the treatment actually received.

Safety Population

The safety population will include all participants who received any study treatment. All safety analyses will use the safety population. Participants will be analyzed according to the treatment they actually received, regardless of the treatment assigned.

Per-protocol (PP) Population

The PP population is a subset of the ITT population who completed the study without any major protocol violations. Analyses will exclude the following randomized participants: (83) those who did not receive TSR/LAVR surgery as planned; (84) those who died within 12 months of surgery and were not assessed on the primary outcome before their death; (85) those who withdrew from study and withdrew consent for use of their data.

Full Analysis Set (FAS)

The FAS will include all randomized participants who receive any study treatment and have at least one assessment since the baseline visit. Participants will be analyzed in their randomized treatment assignment, regardless of the treatment actually received.

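### Late-onset adverse-event percentages may be biased low, because treated women stay in the safety denominator after adverse-event recording has ended for those who leave

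*Combined protocol and SAP*

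**What the plan says.** Five parts of the combined protocol and SAP bear on this.

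- **Population (9.3).** "The safety population will include all participants who received any study treatment. All safety analyses will use the safety population". Women are analysed by the treatment they actually received.
- **Summary method (9.4.4).** "Events will be summarized cumulatively through the following time points: 2 weeks, 2 months, 12 months, and 24 months postoperatively". The section then states: "In addition, the frequency and percentage of participants who had a Serious AE (SAE) or a related AE will be tabulated separately". It says of other safety endpoints: "Any endpoints that relate to safety will be analyzed using methods previously described". It names no denominator for the percentages and no number at risk, person-time rate or censoring rule.
- **Recording window (8.3.4).** Events are recorded if they start after consent and "until 7 (for non-serious AEs) or 30 days (for SAEs) after the last day of study participation".
- **Women who leave (7.2 and 7.3).** A woman who leaves after surgery is not replaced. A woman lost to follow-up is treated as withdrawn.
- **Expected loss (9.2).** "Projecting a 20% dropout/loss to follow up rate over 2 years", the plan raises 96 evaluable patients to 120 recruited. It gives no time pattern. The only hint is a worry that loss could exceed 20% near the end of follow-up.

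**The concern.** A woman who leaves remains in the safety population, but an event that starts after her recording window cannot enter the numerator. A cumulative percentage over all treated women therefore counts her as event-free for the rest of the 24 months. The later an event tends to arise, the more of its occurrences are missed.

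This matters because section 3 makes comparative safety a secondary outcome, and section 4.1 names peri-operative and postoperative complications as an objective. The trial compares a mesh with a mesh-free operation, and section 2.3.1 lists mesh erosion and fistula among the risks. To the extent that such events appear late, they fall where ascertainment is thinnest. If loss also differs between the arms, the arm with more loss will look safer than it is.

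**Working it through.** **The plan's own figure.** 96 / (1 - 0.20) = 120, so the projected 20% loss reproduces the recruitment target. With 1:1 allocation (6.3) this is 60 women per arm, if all 120 are treated.

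**Inputs from the documents.** 20% loss over 24 months (9.2); recording ends 7 or 30 days after exit (8.3.4); the safety population is everyone treated (9.3).

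**Assumptions.** The projected loss occurs after surgery; those who leave have the same event risk as those who stay; the event hazard is constant within the window, with a true risk of 10% over that window; dropout follows one of the patterns below.

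**Formula.** Let f(t) be the density of first events and G(t) the share of treated women still under AE recording at month t. The relative shortfall is

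1 - [integral of f(t)G(t) dt] / [integral of f(t) dt].

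When events are not common, f is nearly flat and the shortfall is close to the average of 1 - G(t) over the window. Ignoring the extra 7 or 30 days:

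- Steady dropout, G(t) = 1 - 0.2t/24. Months 0-24: 0.2 x 12/24 = 10%. Months 2-24: 0.2 x 13/24 = 10.8%. Months 12-24: 0.2 x 18/24 = 15%.
- All gone by month 2. Months 0-24: 0.2 x 22/24 = 18.3%. Later windows: 20%.
- All leave at month 12. Months 0-24: 0.2 x 12/24 = 10%. Months 12-24: 20%.
- Dropout spread over months 12-24. Months 0-24: 0.1 x 12/24 = 5%. Months 12-24: 10%.
- Dropout in the last month only. Months 12-24: 0.1 x 1/12 = 0.8%.

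The full integral, with 30 to 0 days of extra recording, gives these relative shortfalls:

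| Dropout pattern (20% in total) | Events over 0-24 months | 2-24 months | 12-24 months |
|---|---|---|---|
| Steady | 9-10% | 10-11% | 14-15% |
| All by month 2 | 17-18% | 19-20% | 20% |
| All at month 12 | 9-10% | 10-11% | 18-20% |
| Spread over months 12-24 | 4-5% | 4-5% | 8-10% |
| Last month only | under 1% | under 1% | under 1% |

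**Dilution by early events.** Under steady dropout, if 0%, 25%, 50% or 75% of all events fall in the first 2 weeks (assumed shares), the shortfall in the overall 24-month percentage is about 10%, 8%, 5% or 3%.

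**Absolute size.** At a true late risk of 10%, 60 x 0.10 = 6 women per arm have an event. A 10% shortfall misses 0.6 of a woman (9.0% reported); a 20% shortfall misses 1.2 (8.0% reported).

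**Unequal loss, for illustration only.** Suppose 10% leave one arm and 30% the other, which is an assumption without support in the documents. With steady dropout, equal true risks in months 12-24 would appear as a ratio of (1 - 0.1 x 0.75) / (1 - 0.3 x 0.75) = 0.925 / 0.775 = 1.19. If all leave before month 12, the ratio is 0.9 / 0.7 = 1.29.

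**The case against.** **The denominator is inferred.** Section 9.4.4 does not name it, and 9.3 defines a population, not a denominator at each time point. Section 9.4.1 leaves implementation to a SAP written before database lock. This stands, which is why the point is conditional. Still, 9.3 is the only text that governs the safety percentages, and no at-risk alternative is offered.

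**The effect is small in absolute terms.** This also stands. At 10% of 60 women the 95% sampling margin is 1.96 x sqrt(0.1 x 0.9 / 60), about 7.6 percentage points, against a bias of 1-2 points.

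**Most listed events are early.** Many of the specific events in section 8.2 are intra-operative or arise soon after surgery, and peri-operative morbidity is recorded up to the 2-week visit. A reader might infer that the whole cumulative 24-month percentage is 10-20% too low. The documents do not support that: early events dilute the shortfall, and 10-20% needs an assumed dropout pattern that the plan does not give.

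**Other routes and safeguards.** Events can also surface when a woman presents for care (8.3.4) or through her electronic record (10.1.9.1). But the window in 8.3.4 is set by the event's start date, so these routes do not extend it. The DSMB sees dropout rates alongside AE summaries by arm (8.3.5), which helps oversight but does not adjust the reported percentages. The methods that 9.4.4 points back to are the CMH test and mixed models for a binary outcome, and neither handles AE follow-up time. The sensitivity analysis for dropout in 9.4.2 covers the primary endpoint only, and the time-to-recurrence measure in 8.1 concerns efficacy.

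**Conclusion.** The point holds in a limited form. If the safety population is the denominator at every time point, percentages for late-onset events are biased low, and nothing in the plan corrects this. The relative shortfall is about 10-15% with steady dropout, at most about 20% if all leave early, 4-10% if dropout falls in months 12-24, and under 1% if it comes only at the very end. These figures rest on assumed dropout timing, a constant hazard and equal risk in leavers and stayers. At an assumed 10% late risk the loss is about one woman per arm at most. Peri-operative rates are little affected.

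A reader might also infer that one particular arm will be made to look safer. The documents give no dropout figures by arm, so only the possibility of a distorted comparison can be stated. The primary result is not touched. The change is worth making because comparative safety is a declared objective and the remedy is cheap.

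**What to change.** In section 9.4.4, keep the crude counts over all treated women. For the 12- and 24-month time points, add by arm:

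1. the number of women still under AE ascertainment;
2. either cumulative incidence (Kaplan-Meier, or Aalen-Johansen with death as a competing event), censored at the end of AE ascertainment, or events per 100 woman-years of observed follow-up;
3. the between-arm difference from item 2 with a 95% CI.

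Censor at the point that 8.3.4 sets for the type of event (7 days after exit for non-serious AEs, 30 days for SAEs).

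The cost is a few extra tables, prespecified before database lock. Time of onset is already collected (8.3.4). Appendix E lists a study-exit form (Form 20) by title only, and 7.2 mentions only the reason for leaving, so confirm that Form 20 or the last-contact record gives the exit date.

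There are two limits. Intervals will be wide for rare events. The estimates also assume non-informative censoring, so they do not remove bias if women leave because of an adverse event; the numbers under ascertainment at least make unequal loss visible.
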